AddInfoConsiderations	FW_NO-POPPY IRB question.pdf	Reliance Discussion - UTHSC enrollment complete	0.259	[name]	2/10/2022 1:14:38 PM
AddInfoConsiderations	Contact Information and Tracking sheet.pdf	Contact information and tracking sheet, email address added	0.103	[name]	1/22/2021 9:33:23 AM
DataCollection	No Poppy REDCap project.pdf	REDCap project 1-22-2021	1.271	[name]	1/22/2021 8:51:48 AM
DataCollection	Data collection study activity table 1-7-21.pdf	Data collection table different cohorts vs. SOC	0.077	[name]	1/7/2021 12:19:56 PM
DataCollection	Well baby infant demographics data collection form.pdf	Control group data collection form	0.040	[name]	1/7/2021 11:59:05 AM
AddInfoConsiderations	Video Release Update 8.26.2020 bmw.docx		0.014	[name]	8/26/2020 8:45:21 AM
AddInfoConsiderations	NoPOPPY UT IRB approval thru 3-18-21.pdf	UTHSC's IRB approval through March 2021	1.110	[name]	8/20/2020 9:42:24 AM
AddInfoConsiderations	43976 [name] NO POPPY IAA UK-UTK-fullyexecuted7.13.2020.pdf	IAA UK-UTK	0.251	[name]	7/13/2020 2:53:34 PM
AddInfoConsiderations	SCOPE OF WORK from SRAS.pdf	Scope of Work from SRAS	0.378	[name]	2/13/2020 3:40:28 PM
AddInfoConsiderations	UTHSC combined logs (templates).pdf	Logs to be completed by UTHSC	0.410	[name]	2/13/2020 2:58:44 PM
AddInfoConsiderations	Completed UTHSC CVs Med Lic FD and GCP log - Template option 1 (version 021918).xlsx	HSP training log for UTHSC site	0.188	[name]	2/13/2020 2:55:18 PM
AddInfoConsiderations	UK communication plan.pdf	UK communication plan	0.282	[name]	2/13/2020 1:13:25 PM
-Letter of Support & Local Context	UTHSC Local Context Information 20200121.pdf		0.674	[name]	2/12/2020 2:09:37 PM

↳ -Letter of Support & Local Context	19_3181 Signed Subrecipient Commitment Form to University of Kentucky.pdf	Letter of support UTHSC and UK	1.322	[name]	2/12/2020 2:08:42 PM
↳ AdditionInfoConsiderations	UK Relying Site Survey.pdf	UTHSC/UK Relying Site Survey	0.196	[name]	2/6/2020 10:57:59 AM
↳ AdditionInfoConsiderations	Tennessee Code Annotated and Research.pdf	Tennessee Code Annotated (TCA) and Human Subject Research	0.190	[name]	2/6/2020 10:56:31 AM
↳ AdditionInfoConsiderations	SOP informed-consent.pdf	UTHSC SOP informed consent (2)	0.165	[name]	2/6/2020 10:55:28 AM
↳ AdditionInfoConsiderations	NO-POPPY UT Reliance - [name] - FULLY Executed SMART IRB LoA and Supp Agreement.pdf	UK/UTSHC Reliance Agreement	0.710	[name]	2/6/2020 10:54:37 AM
↳ AdditionInfoConsiderations	C3-0050-Informed_Consent SOP for UK.pdf	UTHSC SOP for informed consent	0.089	[name]	2/6/2020 10:54:13 AM
↳ Funding_ProcessDODSOP	SOPadditional-protections-for-children.pdf	UTHSC- SOP for children	0.143	[name]	2/4/2020 12:14:33 PM
↳ StudyDrug	MORPHINE package insert approved with initial review.pdf		0.459	[name]	2/3/2020 10:48:45 AM
↳ StudyDrug	CLONIDINE package insert approved with initial review.pdf		0.453	[name]	2/3/2020 10:48:34 AM
↳ ResearchProcedures	NOPOPPYalgorithm_edited_7.25.19.pdf	Updated Algorithm to align with protocol for research medication	0.129	[name]	9/20/2019 2:40:30 PM
↳ StudyPopulation	breakdown chart of study population.pdf		0.040	[name]	8/9/2019 6:57:50 AM
↳ DataCollection	No-POPPY Study Blood Collection Information Sheet.pdf	Blood collection sheet	0.118	[name]	6/10/2019 7:17:50 AM
↳ AdditionInfoConsiderations	Administrative supplement full proposal_Oct 2018.pdf	NIDA full proposal for additional sample analysis	0.337	[name]	6/7/2019 7:19:34 AM
↳ AdditionInfoConsiderations	Administrative supplement approval from NIDA_Oct 2018.pdf	NIDA approval for additional sample analysis	0.110	[name]	6/7/2019 7:18:52 AM
↳ AdditionInfoConsiderations	Memo to IRB regarding storing samples.pdf	Memo for the IRB regarding additional sample analysis	0.503	[name]	6/7/2019 7:18:34 AM
↳ Advertising	NACU_vs_Study_compared 11-29-18.pdf		0.037	[name]	11/29/2018 9:27:36 AM
↳ StudyDrug	complete_Form O_morphine.pdf	Form O Morphine	0.299	[name]	8/2/2018 12:56:15 PM
↳ StudyDrug	complete_Form O_Clonidine.pdf	Form O Clonidine	0.475	[name]	8/2/2018 12:56:02 PM
↳ GrantContract	3942049_Egrant.pdf	NIDA grant submission	3.188	[name]	8/2/2018 12:52:32 PM
↳ Advertising	Research Flyer NOPOPPYAPPROVED.pdf	Approved Flyer	0.153	[name]	3/14/2018 3:09:26 PM
↳ DataCollection	Order of Maternal Interviews.docx	Maternal Interview Measurement Items	0.013	[name]	2/22/2018 12:12:55 PM

Protocol Changes

Click link to sort [Changed Date](#)
 HIPAA HIPAAIdentificationCertForm changed by [name] on 12/16/2024 11:58:21 AM
 N
 Informed Consent ElectronicConsent changed by [name] on 12/16/2024 11:57:49 AM
 N
 Research Attributes ClinicalResearch changed by [name] on 12/16/2024 11:58:48 AM
 X
 Research Attributes EpidemiologicBehavioralStudies changed by [name] on 12/16/2024 11:58:48 AM
 N
 Research Attributes MaterialOfHumanOrigin changed by [name] on 12/16/2024 11:58:48 AM
 Y
 Research Attributes OutcomesHealthServicesResearch changed by [name] on 12/16/2024 11:58:48 AM
 N
 Research Attributes PatientOrientedResearch changed by [name] on 12/16/2024 11:58:48 AM
 Y
 Research Sites MultisiteLeadInvestigator changed by [name] on 12/16/2024 11:58:27 AM
 *

Study Personnel Changes:

Status	PPIdentity	ProtocolID	PersonID	RoleInProtocol	IsContact	LastName	FirstName	Email	DeptCode	RoomBuilding	SpeedSort	PhoneNum	DeptDesc	AuthorizedConsent	ResponsibilityInProject	Degree	Rank	StatusFlag	IsRemoved	ModBy	ModDate	SFI	IsPRN	MiddleName
Inserted	971680	101597	12595152	SP	N	[name]	[contact]						N	Co-Investigator	PhD	P	N	[name]	12/16/2024 12:00:56	N			

No comments

Statistical Analysis Plan NCT03396588

Based on Consolidated Standards of Reporting Trials (CONSORT) standards, baseline demographic variables were summarized for morphine and clonidine treatment. Frequencies (%) are presented for categorical variables and either mean (SD) or median (min, max) for continuous variables. For outcome results, we present 95% confidence intervals (CIs).

A log-rank test was used to compare treatment arms regarding LOT and LOS. To use data from infants withdrawn from the study, the time of withdrawal was specified as the censoring time. Cox proportional hazards regression modeling was used in a follow-up analysis using treatment and selected risk factors associated with NOWS severity (birth weight, gestational age, gender, cesarean delivery, maternal psychiatric disorder, inborn status, MOUD, other opioid, and non-opioid substance use). Because smoking was highly prevalent and alcohol use was infrequent, they were not included in the model. In post hoc analyses, a negative binomial regression was used to model LOT for 115 infants, excluding those withdrawn from the study. Empirical SE estimates were employed to ensure valid inference.

Treatment arms were compared regarding the need for adjunct medication using frequencies (%) and χ^2 tests. Of 5 infants withdrawn, only 1 received adjunct medication; the other 4 were observed for <2 days. Utilizing data from all 120 infants, we assumed that the 4 infants did not require adjunct treatment. We also removed these 4 infants in a follow-up analysis. The remaining 116 infants were used to fit a logistic regression model, from which adjusted odds ratios were derived.

Wilcoxon rank tests were used to compare treatment groups regarding the timing between initial and final NNNS assessments and the NNNS scores (initial, final, and change). P values were adjusted using the false discovery rate method because of multiple comparisons across 13 summary scores. Intention-to-treat analyses used all available data based on treatment assignment. All tests were 2-sided, with a statistical significance of $P < .05$. Analyses were conducted in SAS v9.4 (SAS Institute Inc 2013. SAS/ACCESSVR 9.4 Interface to ADABAS: Reference. Cary, NC: SAS Institute Inc.).

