
action is not specific to the underlying pathogenesis in opiate withdrawal. Moreover, phenobarbital or benzodiazepines, acting by blockage of N-methyl-D-aspartate receptor-mediated excitation and as agonists to gamma aminobutyric acid (GABA) subtype A receptors, have been shown to impair cell proliferation and inhibit neurogenesis.⁴²

In the original pilot trial, we selected clonidine as an alternative, since clonidine as an α2-adrenergic agent, acts on the central sympathetic activity, which has been shown to be increased with opiate withdrawal. Prolonged opiate exposure results in activation of opiate receptors in the locus ceruleus, which contain clusters of noradrenergic cells. Opiate exposure decreases adenylyl cyclase activity, reducing cAMP levels.⁴³⁻⁴⁵ Such effect on cAMP results in an increase in potassium efflux with associated decrease in calcium influx; these processes are inhibitory to brain noradrenergic activity.^{46,47} With cessation of opiate supply, the inhibitory effect of chronic opiate on noradrenergic activity is lost resulting in increased noradrenergic activity.⁴⁸ Clonidine, an α2 adrenoreceptor agonist has inhibitory effects on noradrenaline release in the locus ceruleus; its administration decreases noradrenergic neuronal activity and consequently decreasing withdrawal manifestations. Clonidine has previously been reported as a single drug therapy for NAS,^{49, 50} and recently as an adjunct to morphine.¹⁸ If administered with choral hydrate⁵¹ the duration of treatment for NAS is shorter compared to morphine plus phenobarbital. It has been used in neonates post operatively to prevent NAS.⁵² Because of the potential effects of continued opiate use on the developing brain, we propose to evaluate the use of clonidine in the treatment of NAS.

In this current proposal, the research plan is based on our pilot study, ⁶² which randomized infants with NAS, >35 weeks' gestational age, to receive morphine (n=15) or clonidine (n=16). The treatment groups were similar as to mean birth weight, gestational age, Apgar scores, and postnatal age at treatment. Infants enrolled had no other medical or surgical complications. Treatment was initiated per our NICU standard at the time, and will be continued in this protocol. Total LOS was shorter by about 1 week in the clonidine (mean of 15 days), compared to 21 days in the morphine group. (See NIH protocol for additional information, page 3-4).

Addendum:

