Attachments

Attach Type	File Name
Advertising	Research Flyer NOPOPPYAPPROVED.pdf
Advertising	NACU_vs_Study_compared 11-29-18.pdf

Research Procedures

Describe how the research will be conducted.

- What experience will study participants have?
- What will study participants be expected to do?
- How long will the study last?
- Outline the schedule and timing of study procedures.
- Provide visit-by-visit listing of all procedures that will take place.
- Identify all procedures that will be carried out with each group of participants.
- Describe deception and debrief procedures if deception is involved.

Differentiate between procedures that involve standard/routine clinical care and those that will be performed specifically for this research project. List medications that are explicitly forbidden or permitted during study participation.

Initially, for an opiate-exposed neonate, behavioral care is started (quiet room, swaddling, ad lib feeding, vestibular movement). After an infant is admitted to Kentucky Children's Hospital with suspected NAS or at risk for NAS, standard care is to monitor for signs of withdrawal to determine the need for treatment. Currently, babies are prescribed an opiate replacement per medical provider discretion.

Cohort 1: After consenting, when the baby requires treatment, an order will be written to initiate treatment and the pharmacy will receive orders to randomize. The infant will be randomized to receive oral morphine or oral clonidine. Randomization will be done by Investigational Drug Services Unit (IDS) using computerized randomization. Kentucky Children's Hospital personnel administering the drug will be blinded to the treatment. Drug will be prepared and dispensed in similarly appearing solutions and volumes. Newborns requiring a second drug to help relieve the symptoms will be treated with either the opposite research medication being used and/or phenobarbital for both groups and at attending discretion.

Morphine Therapy:

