The research team will perform an assessment within the first few days after treatment is initiated, using the NICU network neurobehavioral scale (NNNS)57. Examiners administering NNNS are trained and certified, and will be blinded to treatment received. A second NNNS exam will be performed when the infant has been weaned off of study medication before discharge. The secondary site at UTHSC will perform the NNNS-2 in lieu of the NNNS, this is a shortened version that has been tested for validity and reliability.

Monitoring and data collection of clinical status while on the study will include documentation of interval FS, changes in dosing (increase, decrease, etc), observation for side effects such as drowsiness and apnea with either treatment, monitoring heart rate and blood pressure at least every 8 hours, until maximum dose is reached. Drug concentrations will be obtained at various times, depending on standard lab draws. Finnegan scoring will continue to be monitored after tapering of dosage has been started. Review and data collection of infant and maternal records will be done to obtain prenatal history, pregnancy history, and on-going medical history. When possible and prior to discharge, caretaker interview will be done for detailed substance use inventory during pregnancy (legal and illegal drugs, and medication) Addiction Severity Index, information to derive the Hollingshead's socio-economic status (SES) and tracking information, as well as paternal and neighborhood characteristics. However, while all attempts will be made to obtain a caretaker interview while the patient is in the hospital, this is an unpredictable and not always stable population and their presence at bedside is not always guaranteed. Discharge data collection will include infant discharge diagnosis and neonatal complications, Child Protective Services involvement, and discharge disposition.

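### The follow-up Cox model for LOT and LOS adjusts for indirect correlates of withdrawal severity but not for the pre-dose Finnegan score or age at first dose, and may lose precision

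*Combined protocol and SAP*

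**What the plan says.** The SAP's first comparison is unadjusted: "A log-rank test was used to compare treatment arms regarding LOT and LOS". The adjusted model comes second, a Cox regression presented as a follow-up analysis "using treatment and selected risk factors associated with NOWS severity (birth weight, gestational age, gender, cesarean delivery, maternal psychiatric disorder, inborn status". The full covariate list is "birth weight, gestational age, gender, cesarean delivery, maternal psychiatric disorder, inborn status, MOUD, other opioid, and non-opioid substance use", nine in all. An exclusion is explained for two variables only: "Because smoking was highly prevalent and alcohol use was infrequent, they were not included in the model". The Finnegan score and age at first dose are not mentioned.

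The protocol ties the Finnegan score closely to the outcome:
- The description of the cohorts separates treated from untreated exposed infants on Finnegan scores.
- Under Research Procedures, "standard care is to monitor for signs of withdrawal to determine the need for treatment", and randomisation follows once treatment is needed.
- The morphine and clonidine paragraphs make escalation, stabilisation, weaning and stopping all depend on scores below 8.
- The Resources section says that Finnegan scoring is routine and that nurses are retrained every six months.
- Study data capture is described as follows: "Monitoring and data collection of clinical status while on the study will include documentation of interval FS, changes in dosing".

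Age at start of treatment appears in the account of the pilot study: "The treatment groups were similar as to mean birth weight, gestational age, Apgar scores, and postnatal age at treatment".

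**The concern.** The model is meant to adjust for severity of withdrawal, yet it relies on correlates of severity and leaves out the trial's own measure of it. LOT is largely the time an infant needs to bring scores below 8 and keep them there during the wean, so the protocol itself gives a structural reason to expect the starting score to predict LOT. Age at first dose should vary too. Some infants develop symptoms within days of birth, others arrive by referral during the first week, and about 40-50% of NAS admissions at the lead site are referred.

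In a Cox model, leaving out a prognostic baseline variable moves the treatment hazard ratio toward 1 even when the arms are balanced, and it lowers power. At stake are the size and precision of the adjusted hazard ratio, and the reader's ability to see whether the arms started with similar severity.

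**Working it through.** **Inputs from the SAP.** 120 infants; 5 withdrawn and censored at withdrawal, so 115 completed courses; nine covariates; two-sided 0.05.

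**No figure to reproduce.** The documents give no power or effect size for the Cox model. The one sample-size figure, 250 treated infants, comes without alpha, power, effect or SD, and this point does not need it.

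**Assumptions.** 1:1 allocation (the ratio is not stated). Exponential times. The nine covariates are independent standard normals with log hazard ratio 0.1 per SD each. The two omitted variables are independent of the nine, with log hazard ratio g per SD each. The model is

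hazard = h0 × exp(ln(HR) × arm + 0.1 × (Z1 + … + Z9) + g × (W1 + W2)).

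On the hazard-ratio scale, g = 0.2, 0.3 and 0.5 are e^0.2 = 1.22, e^0.3 = 1.35 and e^0.5 = 1.65 per SD. HR above 1 means an earlier end of treatment in one arm.

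**Results** (2,000 to 3,000 simulated trials per row; without = nine covariates, with = nine plus two):

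| True HR | g | Mean HR without | Mean HR with | Power without | Power with | Difference (points) |
|---|---|---|---|---|---|---|
| 1.4 | 0 | 1.44 | 1.45 | 42.5% | 42.4% | -0.1 |
| 1.4 | 0.2 | 1.42 | 1.45 | 39.2% | 41.8% | 2.6 |
| 1.4 | 0.3 | 1.38 | 1.45 | 36.2% | 41.9% | 5.7 |
| 1.4 | 0.5 | 1.33 | 1.45 | 29.2% | 43.8% | 14.6 |
| 1.8 | 0 | 1.90 | 1.92 | 85.1% | 84.3% | -0.8 |
| 1.8 | 0.2 | 1.82 | 1.90 | 80.6% | 83.4% | 2.8 |
| 1.8 | 0.3 | 1.77 | 1.90 | 75.2% | 83.0% | 7.8 |
| 1.8 | 0.5 | 1.64 | 1.90 | 63.4% | 82.8% | 19.4 |

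A second set of runs gave, at HR 1.8, 80% v 85%, 76% v 85% and 64% v 84% for g = 0.2, 0.3 and 0.5. Over both hazard ratios its losses were about 4 to 9 points at 0.2-0.3 and 13 to 20 points at 0.5. Taking the two sets together, the loss is about 3 to 9 points at 0.2-0.3 and about 13 to 20 points at 0.5.

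**No treatment effect (HR 1.0).** The mean hazard ratio stayed at 1.00, to within 0.01, for every g in both models. Type I error was 6.8% to 7.4% with nine covariates and 6.8% to 7.7% with eleven. The slight excess over 5% therefore comes from fitting many terms to 115 events, and it is already present in the nine-covariate model. The same holds for the slight overestimate of HR in the fuller models (1.44 to 1.45 for a true 1.4).

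**Chance imbalance.** With 60 per arm, the standardised difference in a baseline variable has standard error √(2/60) = 0.18, so differences up to 1.96 × 0.18 = 0.36 SD are ordinary. At g = 0.5 such a difference moves the log hazard ratio by 0.5 × 0.36 = 0.18. No imbalance is documented; this only shows why the variables are worth tabulating.

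**The case against.** The strongest reply is that this is a covariate preference in a secondary model. Much of it stands.

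- A reader might infer that the main comparison of LOT and LOS is diluted. The documents do not support that. The main comparison is the log-rank test, which uses no covariates, and adding Cox terms changes nothing in it.
- A reader might infer that the dilution is an established fact. Its size depends on a prognostic strength that the documents do not give. Every treated infant had already met a treatment threshold, which may narrow the spread of pre-dose scores, and the nine covariates may carry part of the information (inborn status for age at start, for example). With g = 0 there is no gain and up to about one point of cost.
- A reader might call this confounding. Under randomisation it is the gap between a conditional hazard ratio and one averaged over the omitted variables, and it vanishes when there is no effect.
- A reader might extend the point to the logistic model for adjunct medication, or say that the baseline table omits both variables. The SAP lists neither that model's covariates nor the baseline variables, so neither omission is shown.
- A reader might assume that both variables are already in the study database. Pre-dose scores must exist clinically, but the protocol's wording on data capture covers scores while on study. For infants referred from other nurseries, part of the pre-dose window may precede admission. Age at first dose is named only for the pilot, although it follows from birth date and treatment start. The data collection forms are attachments that are not shown.

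The objection about overfitting carries little weight, because simulated type I error was about 7% with or without the two extra terms. What the reply does not answer is why a model built to adjust for severity leaves out the trial's own severity score without a stated reason.

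**Conclusion.** The point holds as a conditional one about the follow-up Cox model. Neither the pre-dose Finnegan score nor age at first dose is among its nine covariates, and the omission is unexplained. If they predict LOT beyond those nine, the hazard ratio is pulled toward 1: at a true 1.8, from a mean estimate of about 1.90 with them to 1.82, 1.77 or 1.64 without them at g = 0.2, 0.3 or 0.5. The power lost is about nil, 3 to 9 points, or 13 to 20 points as g goes from 0 through 0.2-0.3 to 0.5. These figures rest on the assumed g, on independence from the other covariates and on 1:1 allocation.

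The log-rank result stands as planned and nothing here makes the existing Cox model invalid. Because the SAP is written with results in hand, any refit can only be a sensitivity analysis. This is a cheap improvement.

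**What to change.** 1. Add two continuous covariates to the Cox model for LOT and LOS: the pre-dose Finnegan score (for example, the mean of the scores available at the treating site in the 24 hours before the first study dose) and postnatal age at the first study dose.
2. Report the refit beside the existing nine-covariate model, labelled as a post hoc sensitivity analysis, with the number of infants in each.
3. Show both variables by arm in the baseline table.
4. List the covariates of the logistic model for adjunct medication. If they also omit these two, and the number of adjunct events allows two more terms, run the same refit there.
5. If the pre-dose scores were not captured or cannot be retrieved, say so in one sentence as the reason for the omission.

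The cost is deriving two variables and rerunning one or two models, with no new patients. The downsides are two more terms on 115 events, a possible loss of referred infants whose scores before transfer are missing, and the post hoc status of the result.
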